---

## **The Study Protocol of the project**

### **Different kinds of acupuncture treatments for Knee Osteoarthritis: a Multi-center Randomized controlled trial**

#### **Research objectives**

(1)The study aims to exam different kinds of acupuncture treatment for treating knee osteoarthritis (KOA), compared with the effective drug control group respectively, and confirm the efficacy of different acupuncture treatments of KOA, and further a safe, effective and easily-spread therapy for KOA.

(2)To observe and compare the effects between groups of different acupuncture treatment: acupuncture group, moxibustion group and warm-needling group, and make clear whether the moxibustion play a key role in the acupuncture treatment for KOA.

(3) To compare the effects of acupuncture group and sham-needle group and make clear whether acupuncture is effective in KOA treatment.

(4) To compare the effects of electro-acupuncture group and the warm-needling group, to explore whether there are different clinical effects of electric stimulation and warm stimulation in acupuncture treatment of KOA.

#### **Research Methods**

##### **Participants**

###### **1. Case source**

360 patients with knee osteoarthritis are planned to be recruited from May 2018 to December 2021 in the following six hospitals: Jiaxing TCM Hospital, The Third Affiliated Hospital of Zhejiang Chinese Medical University, Zhejiang provincial Hospital of TCM, Zhejiang Hospital, Hangzhou Red Cross Hospital ,Zhejiang Provincial Tongde Hospital.

**2. Diagnostic criteria:** The diagnostic criteria of KOA in western medicine refers to the diagnostic criteria of American College of Rheumatology (ACR) and Kellgren-Lawrence Classification; and the TCM diagnostic criteria refers to the Diagnostic efficacy of TCM syndrome.

---

1)The diagnostic criteria of western medicine: Meet the KOA diagnostic criteria, in I-III level of K-L classification.

According to the American College of Rheumatology (ACR) KOA diagnostic criteria:

- (1)Have knee pain of most days in a month;
- (2) There is a noise in the joint activity;
- (3)Morning knee stiffness lasting less than 30 minutes;
- (4)Over 38 years old;
- (5)Bony swelling and snapping sound of the knee joint;
- (6)Bony swelling and no snapping sound of the knee joint.

**At least 1-4 or 1, 2, 3, 5 or 1 and 6 can be diagnosed.**

The grade of knee osteoarthritis was graded, and the grading evaluation criteria of Kellyon-Lawrence (K-L) was adopted (level 5).

0:Normal;

I:Doubtful joint space narrow, possible osteophytes ;

II :Definite osteophytes, possible joint space narrow or normal;

III:Moderate osteophytes, definite joint space narrow, some sclerosis of subchondral bone , possible deformity;

IV:Large osteophytes, marked joint space narrow, severe sclerosis of subchondral bone, definite deformity.

2)The diagnostic criteria of TCM :

(1)For the first time, there was dull pain in the knee joint , with unfavorable flexion and extension of the knee joint; Knee pain released slightly by mild activity, and aggravated when the climate changes, and repeated lingering.

(2)The onset of the disease is slow, often among the middle aged or elderly;

(3)The joints can be mildly swollen, the joints have the kala or the frictions tone during the activity, and the severe ones can see the muscular atrophy and joint deformity;

(4)X-ray examination showed osteoporosis, irregular joint surfaces, narrow joint space, subchondral bone sclerosis, and lip-shaped hyperplasia, osteophyte formation;

(5)Check ESR, anti-chain "O", rheumatoid factors and more to identify with

---

rheumatism and rheumatoid arthritis.

### **3.Inclusion criteria**

- 1)Aged 40-75 years old;
- 2) History of knee pain for more than 3 months, and complain of knee pain on most days of the past month;
- 3) I-III level in K-L classification;
- 4)At visit an average knee pain severity of 4 point or more on an 10-point VAS;
- 5)Volunteer for this test and sign informed consent.

### **4.Exclusion criteria**

- 1) Knee osteoarthritis patients with history of gout, infection, tumor, autoimmune diseases, trauma or other causes of knee pain or knee deformities;
- 2)Patients who have local skin damage, poor skin conditions or coagulant dysfunction and patients who are not suitable for acupuncture;
- 3)Patients who are accompanied with serious medical problems, mental or shallow sensation disorder disorders, cognitive dysfunction or shallow sensation disorder who cannot cooperate with the treatment;
- 4)Patients who have received acupuncture or needle knife in the past month;
- 5)Other patients who are not suitable for acupuncture treatment.

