### **5.Off standard**

- 1)The patient did not follow this test, quit or lost his visit;
- 2)Severe adverse reactions or adverse events occurred during treatment.

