## **7. Clinical Ethics and Clinical Trial Registration**

The study follows the “Helsinki Declaration” and other relevant regulations, the clinical study was carried out after approved by the Central Ethics Committee. Before each subject was enrolled in the study, it was the investigator's responsibility to provide the subject or his agent with a complete and comprehensive introduction of the purpose, procedure, and potential risks of the study, and to sign an informed consent form so that the subject knowing that they have the right to withdraw from this study at any time, informed consent should be retained as a clinical research document. Before collecting the first case, the central ethics approval was completed and the clinical trial registration was completed.

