## **Analysis methods**

### **1. Sample size estimation**

Sample size estimation was by using PASS(version 11.0) software. According to document analysis and trial test, the WOMAC joint function scores could change by  $13.0 \pm 5.6$  after treatment of positive drug control group.(Qilin Liu. Observation on clinical effect of KOA by needling with moxibustion[J]. TCM clinic Research,2016,8(09):108-109.), while needling group changed by  $8.8 \pm 3.7$ (Acupuncture for Chronic Knee Pain A Randomized Clinical Trial), EA group changed by  $8.9 \pm 4.0$ (trial test), Moxibustion group changed by  $10 \pm 4.7$ (trial test), Warm needling group changed by  $12.0 \pm 6.1$ (Jianbo Wang, Yanlin Wang, Yongqi Lu, Yaochi Wu. Effect analysis of KOA by needling with moxibustion[J]. Shanghai acupuncture magazine,2010,29(06):390-392.), Sham acupuncture group changed by  $5.8 \pm 3.0$ (Acupuncture for Chronic Knee Pain A Randomized Clinical Trial). In the condition of  $\alpha=0.05$ , the power of test was  $1-\beta=0.9$  and the six groups were distributed according to 1:1:1:1:1:1 ratio, and the sample amount is at least 42. The sample size is to be expanded by estimated 20% dropout rate, and finally, there are at least 53

---

patients in each group. In view of the equality of the distribution of all cases in six centers, there were a total of 360 cases with 60 patients in each group. The following equation was used:

$$n = \psi^2 \left[ \sum_{i=1}^k s_i^2 / k \right] / \left[ \sum_{i=1}^k (\bar{X}_i - \bar{X})^2 / (k-1) \right]$$

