## 2. Random allocation

The block randomization is operated by the central randomization system (by telephone and online). When the subjects met inclusion exclusion criteria of the study, The randomization of the central random system is conducted by assigned personnel or clinical investigators of each center. The randomization scheme of this study is produced by the Clinical Evaluation and Analysis Center of Zhejiang Provincial Hospital of TCM which is not involved in the statistical analysis of this project . The randomization scheme of this study and The parameters set during the process of the program are called the bottom of the blind, which is generated by the random scheme personnel to sign and seal, and taken care of by the specialized personnel not involved in the project of the Clinical Evaluation and Analysis Center of Zhejiang Provincial Hospital of TCM. The central random system has strict personnel authority, and other than the highest level system management staff, no one has access to the random scheme in the central random system.

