#### **(6)Celebrex group**

Celebrex capsules (Celebrex, Capsules, Pfizer Pharmaceuticals Ltd), which will be applied 1 time daily( 1 time oral 0.2g) for 4 weeks.

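### Every arm is screened for suitability for acupuncture, but no explicit criterion covers Celebrex, which one patient in six is assigned

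*Combined protocol and SAP*

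**What the plan says.** Section 4, Exclusion criteria, raises suitability for acupuncture in two of its five items. Item 2 groups skin problems with "coagulant dysfunction and patients who are not suitable for acupuncture". Item 5 is a catch-all: "Other patients who are not suitable for acupuncture treatment". Item 4 is a washout for recent acupuncture or needle-knife treatment. The nearest general medical item is item 3, which begins "Patients who are accompanied with serious medical problems" and goes on to mental, sensory and cognitive disorders, with a closing qualifier about inability to cooperate with treatment.

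Under Interventions, the Celebrex group takes capsules "which will be applied 1 time daily( 1 time oral 0.2g) for 4 weeks". The general part of the same section also allows Celebrex 0.2 g once daily as rescue for unbearable knee pain and does not restrict this to particular groups.

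On numbers, the sample size section says "there were a total of 360 cases with 60 patients in each group". On timing, the Random allocation section ties randomisation to eligibility: "When the subjects met inclusion exclusion criteria of the study". It describes no further suitability check between meeting the criteria and allocation.

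**The concern.** In a six-arm randomised trial, each patient should be able to receive whichever of the six treatments is drawn. The plan applies this to needling, and applies it even to patients who will be allocated to the drug arm and never needled. It does not apply it to the drug.

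Two things can follow when an unsuitable patient is allocated to Celebrex. Either the patient takes a drug that a screen would have kept from them, or someone withholds it after randomisation and the patient goes without the assigned treatment. The first is a safety matter. The second weakens the drug control arm, against which objective 1 compares the acupuncture treatments. A screen before randomisation avoids both.

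**Working it through.** **The plan's own figures.** The sample size section gives at least 42 per group before dropout. With 20% dropout, 42 / (1 − 0.20) = 52.5, which rounds up to the stated 53. The plan then sets 60 per group: 6 × 60 = 360, as stated. The Celebrex share is 60 / 360 = 1/6.

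**Scheduled exposure.** 4 weeks × 7 days = 28 daily doses of 0.2 g per patient in that arm, before any rescue use in other arms.

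**Criteria set against the drug arm.**

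| Place | Subject | Screens for Celebrex before randomisation? |
|---|---|---|
| Inclusion 1–5 | Age, pain history, radiographic grade, pain score, consent | No |
| Exclusion 1 | Other causes of knee pain or deformity | No |
| Exclusion 2 | Skin, clotting, suitability for acupuncture | Not as a drug screen; clotting may overlap |
| Exclusion 3 | Serious illness; mental, sensory or cognitive disorder | Not as a drug screen; serious illness may overlap |
| Exclusion 4 | Recent acupuncture or needle knife | No |
| Exclusion 5 | Suitability for acupuncture | No |
| 5. Off standard | "Severe adverse reactions or adverse events occurred during treatment" and non-adherence or loss | No; acts after treatment starts |
| 6. Withdrawal criteria | Uncontrolled pain, serious adverse events | No; acts during the study |

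Suitability for acupuncture appears in 2 of 5 exclusion items. Suitability for Celebrex appears in none of the 5 inclusion and none of the 5 exclusion items.

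**How far the overlap reaches.** Clotting disorder in exclusion 2 sits among reasons not to needle. Exclusion 3 turns on seriousness, and its closing qualifier may narrow it to patients who cannot cooperate. On either reading, an otherwise well patient with an allergy or intolerance to the drug need not be caught.

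**What cannot be computed.** If a share p of otherwise eligible patients were unsuitable, 60p would be expected in the Celebrex arm, and about 360/(1 − p) − 360 further otherwise eligible patients would be needed to reach 360. The documents give no p, so neither expression is given a value here.

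**The case against.** The strongest reply is that allocation is not exposure. The plan does not say who prescribes or dispenses Celebrex, and nothing in it tells a site to give the drug against clinical judgement. Rescue use is permitted, not required, so it can be withheld. Before enrolment, the ethics section requires an explanation of the "purpose, procedure, and potential risks of the study", and some unsuitable patients may decline at that point. The consent form is not in the text reviewed, so what patients are told about the drug cannot be judged. Exclusions 2 and 3 also remove some relevant patients from every arm.

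Much of this stands. Exposure is possible but not established, and it would be too strong to say that nothing relevant to the drug is screened. What does not stand is the idea that clinical judgement closes the gap. If it is used only after allocation, the drug is withheld from a randomised patient. Consent informs; it is not an eligibility rule.

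A reader might infer that exposure of at least one unsuitable patient is close to certain. That would come from putting an assumed rate into 1 − (1 − p)^60, which only restates the assumption and counts patients allocated, not dosed or harmed.

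A reader might also infer a biased efficacy comparison, because the full analysis set requires some treatment to have been received and could lose patients who were never dosed. Whether the ITT analysis named under Statistical analysis uses that set is unclear. No size can be given, and the handling of such patients is a separate matter on which this point does not rest.

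**Conclusion.** The point holds as a gap in the eligibility rule. As written, a patient unsuitable for Celebrex can satisfy every criterion and be allocated to it, with either avoidable exposure or post-randomisation withholding as the result. The part of the trial directly concerned is 60 of 360 patients (1 in 6), with 28 scheduled daily doses each; rescue use in other arms is secondary. The number of unsuitable patients among them is unknown.

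The conclusion rests on two readings: that exclusions 2 and 3 give only partial, incidental cover, and that no unwritten suitability check precedes randomisation. The documents establish no harm and no effect on the primary estimate, error rate or power. The case for change is a foreseeable, avoidable problem with a cheap remedy.

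**What to change.** Extend exclusion 5 so that, before randomisation and in all arms, it excludes anyone the investigator judges unsuitable for any of the six allocated treatments, including Celebrex. The clinical team should set the drug-specific contraindications, so that sites have a checkable list and not only a general judgement.

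This can help only patients not yet randomised; planned recruitment ran from May 2018 to December 2021. It requires one amended eligibility line and no change to the sample size. There are two costs. Some more patients will fail screening, in a number that cannot be stated without a rate. The results will also no longer cover patients who cannot take Celebrex, including for objectives 2 to 4, none of which involves the Celebrex arm.

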### **5.Off standard**

- 1)The patient did not follow this test, quit or lost his visit;
- 2)Severe adverse reactions or adverse events occurred during treatment.

### **6.Withdrawal criteria**

- 1)A diagnostic physician at each center assessed the KOA exacerbations that occurred during the study. When a patient develops knee pain that cannot be alleviated by

---

acupuncture (based on VAS score > 8 points), the physician evaluates the severity and discontinues the study;

2) Onset of serious adverse events such as severe infection, coma, shock, death, etc., the main investigator should be reported immediately and the study should be suspended immediately.

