## 4. Interventions

The six groups of participants (except for western medicine group) will be treated with different kinds of acupuncture treatment. **The unified needle** is the single-use, sterile steel, size 0.30×25mm or 0.30×40mm needle(Huatuo brand disposable acupuncture needle, Suzhou Medical Co., Jiangsu, China),it will be used in Ordinary acupuncture group,

---

electro-acupuncture group and Warm-needling acupuncture group; **The unified moxa** is the 2cm Yufu brand Qing Ai(Jiangsu Kangmei Pharmaceutical Co. Ltd. Jiangsu, China,Z32020253 ),it will be used in Mild moxibustion group and Warm-needling acupuncture group; **The unified Electro-acupuncture apparatuses** is the Huatuo SDZ-IIB electro-acupuncture apparatus(Jiangsu Suzhou Medical Supplies Factory LTD. Jiangsu China ),it will be used in electro-acupuncture group; **The unified Leather measuring tape** is: Type 8214 ,Size 1.5m\*7.5mm produced by Deli Group Limited; **The unified acupuncture time and therapy course** were: Each treatment lasts for 30 minutes which will be applied 3 times a week(ideally every 1 or 2 days ) for consecutive 4 weeks, 12 sessions in total; **Operator and attention:** Acupuncture treatments will be operated by the attending doctor and should pay attention to the disinfection of operator's hands and local skin before and after treatment. The treatment of acupuncture and moxibustion will be mainly aimed at the knee joint with pain symptoms, such as single or bilateral knee pain, the treatment of single / bilateral knee joint. **The unified emergency medication and treatment:** If the participants have unbearably knee pain during the study, we will allow them to take temporary emergency medication: oral Celebrex capsules (Celebrex, Capsules, Pfizer Pharmaceuticals Ltd), which will be applied once a day (0.2g a time orally).The situation of drug use should be recorded in detail; swelling of the knee joint during the test and temporary receiving treatment, but it should be recorded in detail. swelling in the knee joint effusion shown during test, allowed to accept fluid pumping treatment, but it should also be recorded in detail.

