### **5. Outcome measurements and observe time point**

All subjects received a clinical evaluation before treatment (baseline), in treatment (2 weeks), after treatment (4 weeks), and during follow-up (3 months, 6 months) at five time points. The primary outcome measurements includes McMaster University Osteoarthritis Index (WOMAC) function score and Visual Analogue Scale (VAS); Secondary outcomes measures including WOMAC pain score, WOMAC stiffness score, the Physical Activity Scale of the Elderly (PASE), knee joint swelling measurement and WHO-BREF quality of life scale.

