## **6. Statistical processing**

- 1)Full Analysis Set (FAS) : a collection of cases that are randomly enrolled and at least treated once.

In the analysis of the main curative effect indexes, the missing value of FAS is processed by LOCF (Last Observation Carried Forward) method, which was observed at the latest point of time. In the Case of secondary curative effect, general situation and safety Analysis, the Available Case Analysis principle is adopted to carry out missing value processing.

- 2) Per-protocol population set(PPS) : a set of cases that meet inclusion criteria and complete treatment according to the test plan. Good compliance with the test scheme and compliance ,no drug use, and the completion of efficacy evaluation(at least the primary efficacy).

- 3) Safety set (SAS) : at least one treatment, and a safety index to record the actual data.

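### The withdrawal rule ends participation on a primary outcome (VAS above 8) and names only acupuncture; it should stop the assigned treatment in every arm and keep the visits

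*Combined protocol and SAP*

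**What the plan says.** The first item of section 6 (Withdrawal criteria) has a diagnostic physician at each center assess exacerbations. It then covers the patient whose pain is not relieved by "acupuncture (based on VAS score > 8 points), the physician evaluates the severity and discontinues the study". So the trigger is a VAS threshold, followed by a clinical judgement.

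The rest of the plan bears on it as follows:

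- Section 5 (Outcome measurements) makes VAS and WOMAC function the primary outcomes. It plans assessments for all subjects at baseline, at 2 weeks, "after treatment (4 weeks), and during follow-up (3 months, 6 months) at five time points". It does not say whether a withdrawn patient is still assessed.
- Section 6 (Statistical processing) says that, for the main efficacy measures, "the missing value of FAS is processed by LOCF (Last Observation Carried Forward) method". The full analysis set (FAS) takes everyone randomized and treated at least once. The per-protocol set requires completed treatment.
- The Statistical analysis subsection analyses the main efficacy measures both per protocol and by intention to treat, and plans loss rates for the six groups.
- Section 4 (Interventions) says "The six groups of participants (except for western medicine group) will be treated with different kinds of acupuncture treatment". The comparator receives Celebrex, "which will be applied 1 time daily( 1 time oral 0.2g) for 4 weeks".
- The first research objective is to test the acupuncture treatments "compared with the effective drug control group respectively".

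**The concern.** Two features of the rule meet in the main comparison.

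First, leaving the study is tied to a high value of a primary outcome. If patients who leave under the rule are not seen again, their later VAS and WOMAC function scores are missing because of how they were doing. LOCF then supplies a score from before or during the exacerbation.

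Second, the trigger is failure of acupuncture, and one arm gets no acupuncture. Read word for word, the rule has no clear meaning for a Celebrex patient, and six centers would each have to interpret it. If they apply it less often in that arm, the two sides of the first-objective contrast lose patients by different rules.

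At stake is the contrast of each acupuncture treatment with Celebrex on both primary outcomes. Outcomes that were never collected cannot be recovered at the analysis stage.

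**Working it through.** **No figure to reproduce.** The documents give no expected number of withdrawals under this rule and no VAS mean or SD. The sample size rests on WOMAC function. Everything numerical below is assumed, apart from 60 patients per arm.

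**Step 1: what LOCF would carry.** A patient stopped before week 2 has only baseline to carry. A patient stopped between weeks 2 and 4 has the week-2 score, or the trigger score if it is recorded as an assessment. The plan does not say that it is. The carried value may therefore be below or above what the patient would later have reported, so the direction of bias is open.

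**Step 2: size under simple arithmetic.** Let a and c be the numbers withdrawn in one acupuncture arm and in the Celebrex arm. Let e be the mean LOCF error in VAS points, assumed equal in both arms and between 1 and 3. Then

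shift in contrast = (a/60 − c/60) × e

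| Application | a v c | e | Shift |
|---|---|---|---|
| Alike | equal numbers | any | 0 |
| Alike | 2 v 1 | 1 | 1/60 × 1 = 0.02 |
| Alike | 6 v 4 | 3 | 2/60 × 3 = 0.10 |
| Not in Celebrex arm | 2 v 0 | 1 | 2/60 × 1 = 0.03 |
| Not in Celebrex arm | 3 v 0 | 2 | 3/60 × 2 = 0.10 |
| Not in Celebrex arm | 6 v 0 | 3 | 6/60 × 3 = 0.30 |

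With an assumed SD of 2, the standard error of a two-arm difference is 2 × √(2/60) = 0.365. A shift of 0.10 is 0.27 SE and a shift of 0.30 is 0.82 SE. With no true difference, a systematic shift of 0.30 would raise the two-sided 5% error to 13.0%, and 0.10 would raise it to 5.9%. If there is no true difference and the rule is applied alike, the expected numbers withdrawn are equal and no shift is expected.

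**Step 3: cross-check by simulation, all values assumed.** Inputs: baseline mean VAS 5.5 to 7.5 with SD 1.3; mean fall 2.5 in one arm and 1.5 in the other; SD 1.2 per two-week step; VAS above 8 at week 2 always withdraws. The difference with complete data is about −0.97.

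| Rule applied in | Withdrawn | LOCF, week-2 (exit) value carried | LOCF, baseline carried | Completers only |
|---|---|---|---|---|
| Both arms | 2–16% v 3–24% | −0.98 to −0.96 | −0.95 to −0.90 | −0.94 to −0.89 |
| Better-responding arm only | 2–16% v 0% | −0.93 to −0.77 | −0.95 to −0.77 | −0.99 to −1.20 |

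Applied alike, the LOCF result moves by at most about 0.07 (0.967 − 0.896). Applied in one arm only, it moves by up to 0.20 (0.976 − 0.774). Completers then move about 0.23 the other way (1.204 − 0.976). That 0.20 at 16% withdrawn implies a mean error of about 0.20/0.16 = 1.3 points, so the 3-point error in Step 2 is a high assumption.

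Both checks agree that even application has a small effect and that uneven application is what could matter.

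**The case against.** The strongest reply is that the rule is a legitimate safety provision, loosely translated, and that the harm is inferred.

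- *Acupuncture may be shorthand for study treatment.* The exclusion criteria bar patients unsuitable for acupuncture from every arm, Celebrex included, and the duty to assess exacerbations is not limited by arm. This stands. A reader might infer that Celebrex patients are exempt, but nothing in the documents says so. The wording permits uneven application; it does not prescribe it.
- *Exit is not automatic.* A reader might infer that any VAS above 8 removes the patient. The text has the physician evaluate severity first, so that reading is too strong. Discretion does not cut the tie to the outcome, however, and it leaves more room for centers to differ.
- *Only treatment may be meant, since section 5 plans assessments for all subjects.* This is possible. But the sentence stands under withdrawal criteria and speaks of discontinuing the study, so leaving the study is the more natural reading. One sentence would settle it.
- *Safeguards exist.* Recorded rescue Celebrex for unbearable pain should reduce the number who reach the rule. Loss rates by group, both analysis sets and a 20% dropout allowance are planned. These limit or expose the problem, but they do not replace scores that were never taken.
- *The effect may be negligible.* This largely stands. If the trigger score is recorded and carried forward, the simulation shows almost no LOCF bias under even application.

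**Conclusion.** The point holds as a stated rule that makes loss depend on a primary outcome, in wording that does not fit one arm of the first-objective contrast. It is not a demonstrated bias.

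Size and direction cannot be obtained from the documents. On assumed inputs the shift is about 0 to 0.1 VAS points if the rule is applied alike. It reaches 0.2 to 0.3 only if the rule is not applied in the Celebrex arm and withdrawals are frequent.

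A reader might take the 0.30-point shift or the 13.0% error as the expected damage. The documents do not support that. It needs 6 of 60 withdrawn against none, which is half of the 20% (12 of 60) allowed for dropout from all causes, and a 3-point error in every one of those patients.

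The change is worth making because it is cheap and fits the planned intention-to-treat analysis. The choice of a primary analysis set, the order of rescue and withdrawal, and the total Celebrex dose in the drug arm are separate matters on which this point does not depend.

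**What to change.** Keep the physician-judged VAS threshold and amend what surrounds it:

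1. Word the trigger as pain not relieved by the assigned treatment, identically for all six arms.
2. Make the consequence a stop of study treatment, not of the study.
3. Keep whichever of the planned 4-week, 3-month and 6-month assessments remain, subject to the patient's right to withdraw at any time (section 7).
4. Use those observed primary values in the FAS. LOCF, which applies only to missing values, is then not needed for them.
5. Report the number stopped under this rule by arm, beside the loss rates already planned.

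The cost is an amendment and a few retained visits at time points already in the schedule. There are two drawbacks. Later scores will reflect whatever treatment the patient receives after stopping. The per-protocol set is not repaired, because patients stopped during treatment still fall out of it.
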